## Study Summary

Title	BRAIN MECHANISMS OF TOPIRAMATE'S EFFECTS ON HEAVY DRINKING
Short Title	Brain Mechanisms of Topiramate
Protocol Number	818988
Phase	N/A
Methodology	Pilot study/Basic Research
Study Duration	Approximately 24 months
Study Center(s)	Single Center, Center for Studies of Addiction
Objectives	

1. Pilot test cue sets and confirm brain and behavioral responses to alcohol cues using pseudo-continuous arterial spin labeling functional magnetic resonance imaging

2a. Demonstrate neuromodulatory effects of a GABA/glutamate modulator, topiramate, on resting baseline and alcohol cue reactivity

2b. Examine the mechanism underlying topiramate's ability to blunt alcohol cue reactivity and reduce heavy drinking days

Number of Subjects	100 enrolled for a target of 40 for main study, up to 10 for the pilot sub-study
Diagnosis and Main Inclusion Criteria	DSM-5 diagnosis of Alcohol Use Disorder
Study Product, Dose, Route, Regimen	Topiramate tablets encapsulate for blinding. Maximum daily dosage is 200 mg by mouth. Six-week titration to maximal dosage.
Duration of administration	8 weeks
Reference therapy	placebo
Statistical Methodology	Frequencies and descriptives; Voxel-wise analyses of cerebral blood flow (CBF) data using a general linear model on absolute and relative CBF

CONFIDENTIAL

This material is the property of the University of Pennsylvania. Do not disclose or use except as authorized in writing by the study sponsor

## 1 Introduction

This document is a protocol for a human research study. This study is to be conducted according to US and international standards of Good Clinical Practice (FDA Title 21 part 312 and International Conference on Harmonization guidelines), applicable government regulations and Institutional research policies and procedures.

### 1.1 Background

Alcohol is the third leading risk factor for premature death and disability [1], as well as a leading cause of preventable cancers [2]. Alcohol dependence affects 18-20 million Americans (i.e. 1 in 12), and alcohol problems cost our society nearly \$225 billion annually [1]. Alcohol dependence is a chronic disorder marked by high rates of relapse. Relapses to drinking are often preceded by a strong desire or craving for alcohol when exposed to alcohol-related stimuli. Knowledge of the mechanisms underlying stimuli- or alcohol cue-induced craving may aid in the search for additional viable pharmacotherapies to help alcohol dependent individuals remain abstinent for life.

Currently, there are three FDA-approved medications to treat alcohol use disorders (AUD): naltrexone, acamprosate, and disulfiram [3]. Empirical evidence suggests that naltrexone reduces the reward properties of and cravings for alcohol [4] and acamprosate supports abstinence [5]; however, their effect sizes compared to placebo are small [6-8]. Disulfiram differs from naltrexone and acamprosate in that it blocks the metabolism of alcohol's primary metabolite, acetylaldehyde, which accumulates in the blood causing unpleasant effects when alcohol is ingested [9]. There is limited evidence of the efficacy of disulfiram, and its potential for toxicity limits its use [10]. These concerns about safety and limited efficacy likely contribute to the fact that FDA-approved medications for AUD are not widely prescribed [7, 11]. Indeed, only 2.8% of patients treated in the Veterans Health Administration who were diagnosed with an AUD received pharmacotherapy [6]. Given these issues and concerns, several medications, other than the currently approved medications for AUD, have been prescribed off label and have shown promise in reducing alcohol consumption.

One promising medication for the treatment of AUD is the GABA/glutamate modulator, topiramate. Although topiramate is FDA-approved as an anticonvulsant, prophylactic treatment for migraine, and for weight loss, both preclinical [12, 13] and clinical studies [14-17] show that topiramate is effective in reducing heavy drinking. Specifically, topiramate reduced alcohol craving [17]; had a moderate treatment effect in reducing heavy drinking in three published placebo-controlled trials [14-16], and appears to have a larger effect size than naltrexone [18, 19] and acamprosate [20]. [name] et al. (in press) found that 200 mg/day of topiramate was well tolerated, reduced the number of heavy drinking days and increased the number of abstinent days more than placebo. In fact, during the last week of the 12-week study, the odds of the placebo group having at least one heavy drinking day was 5.33 times that of the topiramate group. Although these robust findings support the use of topiramate to reduce heavy drinking, the mechanisms underlying its therapeutic effects are not well understood. Thus, the present study aims to elucidate the brain and behavioral mechanisms that mediate topiramate's reduction of heavy drinking.

Functional neuroimaging provides a powerful, non-invasive method to study addictive processes. For example, we, and others, have identified a consistent neural substrate for reactivity to cocaine-, heroin-, cigarette-, marijuana- and alcohol-related cues using a variety of imaging modalities [21-26]. In general, chronic, heavy substance users show greater neural activity in reward-related brain regions, such as the orbitofrontal cortex (OFC), striatum, and anterior cingulate cortex, during drug cue exposure than during non-drug cues. Neuroimaging techniques have also been used to determine how some pharmacotherapies influence factors contributing to substance use. For example, naltrexone has been shown to reduce alcohol cue-induced activation in the ventral striatum (VS) and OFC in non-treatment-seeking alcoholics [27], suggesting that naltrexone's effects are mediated through its reduction of reward-related cue reactivity. To date, there are no published studies examining the effects of topiramate on neural activity or how such effects could be associated with changes in heavy drinking. Based on our own recent finding that topiramate decreased heavy drinking days and increased abstinent days and other research indicating that topiramate reduces heavy drinking days [14-16] and self-reported craving [17], we hypothesize that topiramate may be an effective tool in reducing the reward-related neural activity commonly associated with heavy drinking (i.e., alcohol cue reactivity). Further, our longitudinal, quantitative perfusion fMRI approach, which provides

CONFIDENTIAL

This material is the property of the University of Pennsylvania. Do not disclose or use except as authorized in writing by the study sponsor

for the acquisition of resting brain cerebral blood flow (CBF: ml of blood/100 g of tissue/minute) will provide invaluable information on the mechanisms underlying the ability of a GABA/glutamate modulator to blunt alcohol cue reactivity and heavy drinking.

Neurogenetics is a promising and novel addition to neuroimaging studies. Twin, family and adoption studies indicate that vulnerability to substance abuse is partially inherited. Individual response to medications will most likely be related to genetic phenotypes. Genetics studies, on their own, require huge sample sizes and are expensive; however, when combined with neuroimaging, which offers a 'picture' of individual brains, we can learn why some individuals are vulnerable to alcohol and substance use disorders and why others do not. For example, evidence suggests that the rewarding properties of alcohol involve GABA-ergic, glutamatergic, opioidergic, and dopaminergic neurotransmitter systems. As such, we will focus on genes associated with these systems, such as *DRD4* (D4 dopamine receptor gene), *GABRA2* (GABAA receptor alpha-2 subunit gene), *OPRM1* (mu-opioid receptor gene), and *GRK1* (glutamate receptor, ionotropic, kainate 1 gene) [28]. Further, based on our previous research showing that the C-to-A single nucleotide polymorphism (SNP), rs2832407, in intron 9 of the *GRK1* gene is associated with alcohol dependence [29], this variant in *GRK1* will be our primary focus. Thus, those who have the A allele will likely show the strongest alcohol cue responses.

In summary, the data reviewed above provide strong support for the need to identify the brain and behavioral mechanisms underlying the effects of one of the most prescribed [30], yet poorly understood, medications to treat AUD, topiramate, on key factors contributing to heavy drinking. Given that topiramate 1) has been shown to be effective in reducing heavy drinking [14-17], 2) appears to have a larger effect size than naltrexone [18, 19] and acamprosate [20], and 3) has dual GABAA-mediated inhibitory impulses and AMPA and kainate antagonist effects [31] that likely suppress reward-related mesocorticolimbic dopamine release, we hypothesize that topiramate ameliorates neurophysiological vulnerabilities to heavy drinking by dampening neural activity in the brain at rest *and* during alcohol cue exposure in reward-related brain regions. The current study will elucidate the brain and behavioral mechanisms underlying topiramate's effects and test our hypotheses using a randomized, double-blind placebo-controlled design, pseudo-continuous arterial spin labeling (pCASL) perfusion functional magnetic resonance imaging (fMRI), and other relevant assessments described below. This project will yield novel findings on brain and behavioral responses to alcohol cues, the neuromodulatory effects of topiramate on alcohol cue reactivity, and the mechanisms [resting baseline (RB) modulation] underlying the ability of this GABA/glutamate modulator to blunt alcohol cue reactivity and heavy drinking. Thus, the proposed research, although not a treatment trial, will examine the effects of topiramate on brain and behavior and thereby contribute to medications development and the treatment of AUD.

## **1.2 *Investigational Agent***

Topiramate is an anticonvulsant medication for oral administration approved in the United States for the treatment of seizures and to prevent migraine headaches in adults. The molecular formula is C 12 H 21 NO 8 S and the molecular weight is 339.35. It is designated chemically as 2,3:4,5-Di-O-isopropylidene-β-D-fructopyranose sulfamate. Preclinical studies indicate that topiramate blocks voltage-dependent sodium channels, augments the activity of the neurotransmitter gamma-aminobutyrate at some subtypes of the GABA-A receptor, antagonizes the AMPA/kainite subtype of the glutamate receptor, and inhibits the carbonic anhydrase enzyme, particularly isozymes II and IV. Topiramate absorption is rapid, with peak plasma concentrations occurring at approximately 2 hours following a 400 mg oral dose. The bioavailability of topiramate from the tablet formulation is about 80% compared to a solution and is not affected by food. The mean plasma elimination half-life is 21 hours after single or multiple doses. Steady-state is reached in about 4 days.

According to the FDA-approved labeling, topiramate has been found to be safe at doses of 200mg and 400mg per day in adults.

## **1.3 *Precinical Data***

### Drug-Drug Interactions and Precautions

CONFIDENTIAL

This material is the property of the University of Pennsylvania. Do not disclose or use except as authorized in writing by the study sponsor

Topiramate may have interactions with some antiepileptic drugs and oral contraceptives. Specifically, concomitant use of topiramate with standard antiepileptic drugs (i.e., Phenytoin, Carbamazepine, Valproic acid, and Lamotrigine) has been shown to decrease plasma levels of topiramate. Topiramate may also reduce the efficacy of some hormonal contraceptives (birth control pills, hormonal implants, or hormonal injections). Topiramate does not produce clinically significant additive central nervous system depressant effects in combination with ethanol. Concomitant use of topiramate with other carbonic anhydrase inhibitors (e.g., zonisamide, acetazolamide, or dichlorphenamide) may increase severity of metabolic acidosis and may also increase the risk of kidney stone formation. There is no evidence that topiramate has carcinogenic, teratogenic, or mutagenic potential. Further, topiramate is not reinforcing and is therefore not a drug of abuse.

#### **1.4 Clinical Data to Date**

Topiramate has been evaluated for safety in over 3000 adults, and there are few serious adverse effects associated with topiramate. The most common adverse effect of topiramate compared to placebo is numbness and tingling (49% vs. 6%). The other most common side effects (experienced by 10-31% of patients) in clinical trials include: change in sense of taste, tiredness/sleepiness, fatigue, dizziness, loss of appetite, nausea, diarrhea, weight decrease, difficulty concentrating and difficulty with memory. Cognitive dysfunction adverse effects (e.g., confusion, psychomotor slowing, difficulty with concentration/attention, difficulty with memory, speech or language problems, particularly word-finding difficulties) that were reported during 6-month migraine prophylaxis studies (28% vs. 10% for placebo) were of mild-to-moderate severity. Other adverse effects (experienced by 5-9% of patients) in some clinical trials include: nervousness, slow thinking, abnormal vision, confusion, decreased sensitivity (hypesthesia), anxiety, abdominal pain, dry mouth, involuntary muscle contractions, and language problems. Depression and mood problems have also been reported (experienced by 5-9% of patients). Severe metabolic acidosis (decreased bicarbonate levels) is associated with topiramate treatment in 3-7% of individuals taking the medication.

#### **1.5 Dose Rationale and Risk/Benefits**

##### **Dose Rationale**

The dosage of topiramate selected for this study (200 mg/day) is based on previous research indicating that 200 mg/day is the dosage at which heavy drinkers begin to show therapeutic effects [14-16]. Further, one study of 138 heavy drinkers who sought to reduce their drinking received a 12-week treatment with topiramate (N=67) 200 mg/day or matching placebo and showed that topiramate was well tolerated, with no serious side effects, and was efficacious at reducing heavy drinking days and increasing abstinent days [32].

##### **Potential Risks**

The potential risks of this study include adverse reactions to topiramate, adverse reactions attributable to the combination of topiramate and alcohol, and the small risk incurred by venipuncture. Individuals will be advised to drink adequate amounts of liquid to avoid renal calculi (experienced by 2% of individuals taking the medication). Individuals who are taking carbonic anhydrase inhibitors will be excluded from the study, due to the added risk of metabolic acidosis (decreased bicarbonate levels), which has been reported in 3-7% of individuals taking the medication.

Topiramate is not reinforcing and therefore there is no abuse potential; however, access to topiramate will be strictly limited by the study design and use will be carefully monitored.

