## 3 Study Design

### 3.1 General Design

- **Phase IV Study** - This is a phase IV research study aimed at identifying the brain and behavioral mechanisms underlying the GABA/glutamate modulator, topiramate.
- **Design** – Heavy drinkers who meet DSM-5 criteria for AUD and express an interest in reducing or stopping drinking will be recruited, screened, consented, and if eligible, will complete a randomized double-blind, placebo-controlled study of topiramate ( $N=40$ ; topiramate 200 mg/day:  $n=20$  or placebo:  $n=20$ ). Topiramate or placebo will be initiated after Scan 1 and continued with weekly visits and medical management [33]. During the 7th week, participants will complete Scan 2 followed by medication taper and an endpoint visit. We will use perfusion fMRI during alcohol cue exposure to acquire brain and behavioral responses to alcohol cues. The goals of this study are to pilot test the validity of our alcohol cues and to identify brain and behavioral mechanisms of topiramate in reducing heavy drinking in alcohol dependent individuals.
- **Study Duration** – The duration of this study will be approximately 9 weeks, including screening, Scan 1, 8 weeks of medication and medical management (including medication taper), Scan 2 during week 7, medication taper, and an endpoint visit. The entire study will run for approximately 24 months.

CONFIDENTIAL

This material is the property of the University of Pennsylvania. Do not disclose or use except as authorized in writing by the study sponsor

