**Table 1. Medication Dosing Schedule for Topiramate**

	Medication Dispensed	Morning Dose	Evening Dose	Total Daily Dose
Screening Visit -0	Week 0	No medication	No medication	0 mg
Scan 1/ Visit 1	Week 1	No medication	25 mg	25 mg
Visit 2	Week 2	25 mg	25 mg	50 mg
Visit 3	Week 3	25 mg	50 mg	75 mg
Visit 4	Week 4	50 mg	50 mg	100 mg
Visit 5	Week 5	50 mg	100 mg	150 mg
Visit 6	Week 6	100 mg	100 mg	200 mg
Scan 2/Visit 7	Week 7	100 mg	100 mg	200 mg
Taper Visit 8	Week 8	Reduce dose by 50 mg every 2 days (150 mg for 2 days, 100 mg for 2 days, 50 mg for 2 days, then D/C		
Final visit/Visit 9	Week 9	No medication	No medication	0 mg

If subjects experience significant side effects from the study drug (topiramate or placebo), the investigators will have the option to reduce the dose (number of pills) during the study, based on consultation with the research staff, or as clinically indicated, by interviewing the subject directly. All dosing is on a double blind basis, thus, the physician can vary the number of capsules of placebo or topiramate in response to adverse effects reported by the subject. Upward titration following a dose reduction will be allowed once during the trial. Dose titration, if necessary, will be carefully documented in the study chart along with the clinical rationale.

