## **6.2 Informed Consent and Screening Visit (approximately 4 hours)**

Upon arriving to the Informed Consent and Screening Visit, subjects will be asked to show legal identification and to complete a breathalyzer test to ensure a breath alcohol concentration (BrAC) of 0.00 g%. Reading ability will be evaluated followed by a review of HIPAA privacy laws and the informed consent. Specifically, subjects will be provided a standard HIPAA form that contains privacy laws, and a study staff member will review the consent form with the subject, including an explanation of the study protocol, its risks, potential benefits, and alternative treatment. Following resolution of any questions, subjects who appear to understand the nature of the study and consent will be asked to sign the study consent form. An entire copy of the informed consent form will be given to each subject. S/he is also reminded that the consent expresses willingness to participate but that the subsequent screening process will determine final eligibility. Further, s/he is reminded that participation is voluntary, and at any time, s/he may withdraw from the study.

Following consent, subjects will watch an fMRI video that simulates the experience of undergoing an MRI, meet with the study nurse to complete physical examination and laboratory evaluation, and meet with study staff to complete additional assessments. Baseline laboratory measures include: 1) CBC, 2) Blood chemistries (i.e., standard blood work and lipids), 3) gamma glutamyltransferase (GGTP) to assess the validity of self-reported drinking, 4) HIV test (blood), 5) Electrocardiogram, 6) Urine Toxicology (presence of psychoactive drugs) and 7) for females: a urine pregnancy test and an additional blood sample for biochemical measurement of progesterone and estradiol levels for determination of menstrual cycle phase. A total of approximately 3 tablespoons of blood will be taken. A portion (approximately 2 tablespoons) of this blood sample will also be used to acquire DNA samples from each subject. This portion will be stored for later extraction and analyses. In cases where blood samples are drawn and potential lab errors or abnormal findings occur, subjects will be asked to provide an additional blood sample to repeat the test(s). If the HIV test is positive, the subject will be referred to their primary care provider.

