### **6.3 Laboratory/MRI Session 1 Visit (approximately 3.5 hours)**

Interested, eligible, consented subjects will attend the first of two laboratory/MRI session visits. Prior to each scan visit, subjects will be instructed not to drink alcohol for 24 hours before the scheduled scan session. Upon arrival, subjects will be breathalyzed to ensure that they have not recently consumed alcohol (BrAC = 0.00 g%). During this visit, subjects will complete: 1) brief questionnaires (see Table of Assessments), 2) CogState and CogBias computerized tasks (described below), 3) females will take a urine pregnancy test and provide a blood sample (approximately 2 tablespoons) for biochemical verification of menstrual cycle phase, 4) an MRI scan, and 5) following the scan, a brief medical management session with a nurse to receive medication.

Prior to MRI scanning, subjects will meet with study staff who will conduct the CIWA-Ar and prepare the subject for the MRI session. Subjects will also be asked to drink to satiety prior to starting the scan session to avoid potential confounding effects of thirst on neural responses to cues. During the scanning session, subjects will be asked to lie still with their eyes open for a 5 minute resting baseline scan, followed by two 10-minute audio-visual clips consisting of either alcohol-related cues: individuals differing in race, age and sex who are drinking alcohol and using explicit language designed to induce appetitive desire for alcohol; or non-alcohol-related cues that are similar in content, but individuals relate interesting short stories that do not portray alcohol consumption or alcohol reminders. Subjects will also be asked their level of alcohol craving (on a scale from 0-10) before and after each audio-video clip. Following the scan session, subjects will meet with a nurse to receive their first week of medication and the initial medical management session (see below).

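### Metabolic acidosis is put at 3-7% on topiramate, but no bicarbonate or chemistry test is scheduled between the first dose and the end of the taper, and the dose-reduction rule has no laboratory trigger

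*Combined protocol and SAP*

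**What the plan says.** Section 1.5 (Potential Risks) refers to "metabolic acidosis (decreased bicarbonate levels), which has been reported in 3-7% of individuals taking the medication". Section 1.4 gives the same rate with a stronger label: "Severe metabolic acidosis (decreased bicarbonate levels) is associated with topiramate treatment in 3-7% of individuals taking the medication". Neither section states a dose, a duration, a bicarbonate threshold or a placebo rate.

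The blood tests are set out as follows:

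- **Screening (6.2).** The list includes "2) Blood chemistries (i.e., standard blood work and lipids". Bicarbonate is not named.
- **Visit 1 (6.3).** Women "provide a blood sample (approximately 2 tablespoons) for biochemical verification of menstrual cycle phase". No other draw is described.
- **Weekly visits (6.4, 8.6).** Breath alcohol, weight, vital signs, side-effect and adherence questions; no blood draw.
- **Visit 7 (6.5).** Same procedures as Visit 1, so again a draw for women only, for cycle phase.
- **Visit 9 (6.6, Schedule).** A draw limited to GGTP, after the taper.
- **End of medication (8.6).** A physical examination, laboratory tests that are not defined, and a urine pregnancy test.

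On dosing, 5.2 says: "If subjects experience significant side effects from the study drug (topiramate or placebo), the investigators will have the option to reduce the dose". The sentence goes on to allow reduction after consulting research staff or on clinical grounds, by interviewing the subject. The next sentence ties capsule changes to effects that the subject reports.

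**The concern.** The protocol names a hazard that is defined by a laboratory value and then schedules no laboratory test that could show it while the drug is being taken. The provisions that could act on a low bicarbonate all need a result first. Section 8.1 lets an abnormal diagnostic result count as an adverse event, and 8.6 removes subjects with significant adverse events, but no scheduled on-drug procedure produces the result.

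An acidosis without symptoms would therefore go unseen until dosing was over, and would not start the 5.2 rule. The issue is subject safety rather than bias in the imaging comparison.

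**Working it through.** **Inputs.** Rate 3-7% (1.4, 1.5). Topiramate subjects: 20; all randomized: 40 (5.3). Doses from Table 1, taken for 7 days each week. The 3-7% is a literature rate given without inputs, so there is nothing to reproduce; it is used as stated.

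**Expected cases.** n × p: 20 × 0.03 = 0.6 and 20 × 0.07 = 1.4.

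**Chance of at least one.** 1 − (1 − p)^20:
- 3%: 1 − 0.97^20 = 0.456
- 7%: 1 − 0.93^20 = 0.766

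The population, dose and exposure behind 3-7% are unknown, so half the rate was also tried. It gives 0.3 to 0.7 cases, and 1 − 0.985^20 = 0.261 to 1 − 0.965^20 = 0.510.

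**Dose that could still be avoided.** Weeks 1-7: 175 + 350 + 525 + 700 + 1050 + 1400 + 1400 = 5600 mg. Taper: 2 × (150 + 100 + 50) = 600 mg. Total 6200 mg. The taper is the protocol's own way of stopping, so only dose beyond it counts as avoidable. Two days are assumed for repeat test and review; each further day before the taper costs 200 mg.

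| Draw | Left at draw | Left after 2 days | Avoidable beyond taper |
|---|---|---|---|
| Visit 6, day 1 of Week 6 | 3400 mg | 3000 mg | 2400 mg (39%) |
| Visit 7, day 1 of Week 7 | 2000 mg | 1600 mg | 1000 mg (16%) |
| Visit 7, day 4 | 1400 mg | 1000 mg | 400 mg (6%) |
| Visit 7, day 7 | 800 mg | 450 mg | none; taper has begun |

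The day matters because 3.1 fixes only the week: "Scan 2 during week 7". On day 1 of Week 7 a subject has had 7 days at 200 mg/day. Section 1.2 says "Steady-state is reached in about 4 days", but that is said of the drug, not of bicarbonate. A Visit 6 draw comes before any 200 mg/day dose.

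**False flags.** If the limit cuts off 2.5% of unaffected subjects (assumption; range 1-5%), 40 × 0.025 = 1.0 is flagged without a drug effect (range 0.4 to 2.0). Against 1.0 false flag, and assuming every case is detected, the share of single low values that are real is 0.6/1.6 = 37% to 1.4/2.4 = 58%. At half the rate it is 0.3/1.3 = 23% to 0.7/1.7 = 41%. One unconfirmed value is therefore a weak basis for changing the dose.

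**The case against.** The case on the other side is about weight, not about the missing test.

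- **Other safeguards exist.** Section 4.2 excludes users of carbonic anhydrase inhibitors and people with kidney stones. Adverse events are asked about at every contact (8.2), a physician is always available (8.6), and the principal investigator reviews events at least weekly (10.1). This stands: an acidosis with symptoms could well be noticed and lead to an unscheduled test. It does not reach a case without symptoms.
- **The documents describe the drug as tolerable.** Section 1.2 reports safety at 200 and 400 mg per day. Of a 12-week trial at 200 mg/day with 67 topiramate subjects, 1.5 says it "showed that topiramate was well tolerated, with no serious side effects". Here there are only two weeks at 200 mg/day. This stands, and it limits the severity of the point.
- **The Schedule's laboratory row is poor evidence.** It omits chemistry, and its screening cell is blank although 6.2 requires those bloods. Agreed; the point rests on 6.2 to 6.6.

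A reader might infer three stronger things:

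- **About one severe acidosis is to be expected.** Section 1.4 does say severe, but 1.5 gives the same rate without the word. If 3-7% meant severe cases that would be recorded as serious side effects (an assumption), none in 67 would have probability 0.97^67 = 13% at 3% and 0.93^67 = 0.8% at 7%. That fits poorly at the upper end.
- **The 5.2 rule responds only to complaints.** It also allows consultation and clinical grounds, though through interview and with no laboratory trigger.
- **About a third of the dose could be saved at Visit 7.** The 2000 mg remaining then (32%) includes the 600 mg taper and the days taken by the review.

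**Conclusion.** The point holds in a limited form, at minor to moderate severity. The plan states a laboratory-defined risk and schedules no test for it from first dose to the end of the taper. The undefined tests in 8.6 do not fill the gap, because they come when medication ends and because 6.6 and the Schedule limit the final draw to GGTP.

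The expected count and the 46-77% chance depend on the quoted rate applying to this population, dose and 8-week exposure; at half the rate the chance is 26-51%. How many cases would be without symptoms, and how serious they would be, cannot be derived from the documents. Nothing in them requires bicarbonate monitoring, so the change is recommended as a cheap gain in safety rather than as the correction of a breach.

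There is a separate inconsistency. Section 8.6 requires a physical examination and a urine pregnancy test when medication ends. The Schedule shows the examination only at screening and the pregnancy test last at Visit 7, and 6.6 lists neither.

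**What to change.** 1. Name bicarbonate in the 6.2 screening chemistry, so that each subject has a baseline.
2. Add one on-drug serum bicarbonate for all subjects at an existing visit, and at early withdrawal. Visit 7, fixed to the start of Week 7, is the natural place: a result returned after the visit comes after Scan 2, so acting on it cannot change the scan. Visit 6 or earlier leaves more dose to modify, but a change then could alter the dose at Scan 2. The sponsor should choose and give the reason.
3. Amend 5.2 so that a value below a prespecified limit (for example, the laboratory's lower reference limit) leads to a prompt repeat and, if confirmed, to blinded physician review, dose reduction or early taper, and follow-up to resolution. Keep the values from staff who collect assessments.
4. Make 6.6 and the Schedule list the end-of-medication examination, laboratory tests and pregnancy test required by 8.6, define those tests, and keep the GGTP. Make 1.4 and 1.5 agree on whether the rate refers to severe cases.

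**Cost.** A protocol and Schedule amendment; one inexpensive analyte, twice if the screening panel does not already include it. At Visit 7 the extra venipuncture falls on men only, since women already give blood there. About 1 subject in 40 would need a repeat without a drug effect, under the 2.5% assumption. A low value may partly unblind the reviewing physician. Dose changes after Scan 2 can still affect the Timeline Follow-back data at Visits 8 and 9 and the CogState battery at Visit 9, so they should be recorded for the analysis.
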